#### **5.1** Data Elements

Data elements that may be collected for the FMT registry are shown in Supplements 1-6. In order to make the data elements as broad and inclusive as possible, the FMT Registry Steering Committee developed the data elements based on current guidelines and published recommendations, their own treatment protocols/experience, and feedback from 15 additional large FMT practice sites. *Supplement 1* details the data elements related to FMT technique including donor and recipient screening. For sites that employ a donor questionnaire, *Supplement 2* provides potential questions used on a questionnaire, based on those used for blood transfusion. *Supplement 3* shows the data elements for baseline characteristics of donors and recipients and for FMT treatment indications, while *Supplement 4* provides effectiveness outcomes data elements. Finally, *Supplements 5* and 6 detail data elements for short-term and long-term safety outcomes. Patients will be followed at regular intervals for up to 10 years after FMT for pre-defined and spontaneously reported adverse events and for pre-defined outcomes of effectiveness. Investigators will enter follow-up data at 1 month, 6 months, 1 year and 2 years post-FMT, and patients will then provide data annually up to 10 years.

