#### 6.1 Adverse Events

Based on numerous case reports and small clinical studies in the literature, it appears that FMT for refractory CDI is generally well-tolerated and safe, although occasional adverse events (e.g., febrile

episodes) have been reported. Importantly, a prospective systematic evaluation of both immediate and short-term predefined adverse outcomes in a large number of patients undergoing FMT is currently lacking. In the absence of any consensus guideline on practice standards for FMT in the U.S. and the lack of regulatory oversight for the treatment of refractory CDI, the committee has learned through polling of sites performing FMT that there is a wide variation in the practice of FMT. This variance in practice also raises potential concerns about risks for both short-term and long-term risks. As discussed in section 5.1, to broadly capture adverse outcomes in recipients of FMT that may be indicative of a safety concern, we have developed two data entry fields: 1) Short-Term Adverse Outcomes (within 30 days)—Supplement 5, and 2) Long-term Adverse Outcomes (up to 2 years reported by the physician and 10 years reported by the patient)—Supplement 6. Adverse event information will be provided by the FMT provider site at four time points post-FMT: 1 month, 6 months, 1 year, and 2 years. In addition, patients will be contacted directly by email and text at least annually for up to 10 years to provide follow-up information via a dedicated portal maintained by the Icahn School of Medicine at Mt. Sinai.

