To increase our ability to study unanticipated adverse events, we will include a retrospective control group of patients with recurrent CDI identified from insurance claims using Optum Insight Life Sciences, Inc data. Using these data, we can determine the incidence of relevant outcomes in a group of patients with recurrent CDI treated with antibiotics rather than FMT. The incidence of relevant outcomes in this group can be compared to the patients treated with FMT in the registry. To assure the feasibility of this approach, we have conducted a preliminary analysis of these data to identify the number of patients who will be included in the control cohort. Recurrent CDI was defined as having a physician-made diagnosis of CDI (ICD-9 008.45) treated with 3 separate courses of antibiotics with metronidazole, vancomycin, or fidaxomicin (at least one of which were vancomycin or fidaxomicin). The 3 antibiotic prescriptions had to be at least 10 days apart and the third course needed to be started within the 90 days following the CDI diagnosis. We identified 4,313 patients meeting this definition with mean follow-up of 1.70 years. The sample size should be sufficient to address questions on relatively rare outcomes. For example, at age 68 years (the median age in our control cohort), the probability of death in the next 12 months is 1.75% and the expected survival is 18.8 years (CDC lifetables). With an average follow-up time of 1.70 years, assuming equal number of subjects undergoing FMT and equal follow-up time, we would have 90% power to detect a hazard ratio of 0.77 for a difference in survival rates between FMT and antibiotic treated patients.

As mentioned above, the FMT registry also will support comparative effectiveness studies focusing on different methods of delivery of FMT. Comparative effectiveness studies rely on the ability to adequately account for differences between the treatment groups. The FMT registry will facilitate this by collecting robust data on the indications for therapy and other covariates that describe the recipients and the methods of delivery. Such data will support standard statistical methods including logistic, Cox, and other regression methods, and the development of propensity scores and risk scores for risk adjustment.

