For follow-up beyond 2 years, the ePRO system allows the registry staff to automatically contact the patient for follow-up information. For example, patients can receive an automatic text message or email that opens to a follow-up electronic questionnaire for long-term follow-up. The link to the ePRO also will be embedded in the patient education app that will include content (videos and written information) approved by the steering committee related to FMT indications, preprocedure checklist, potential adverse events, and post-procedure follow-up. The app will be maintained at Sinai AppLab, Icahn School of Medicine at Mount Sinai and will be made available to all FMT patients enrolled in the registry.

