## Supplement 6. FMT Long-term Adverse Outcomes (up to 2 years by physician report and 10 years by patient report)

- Characteristics
  - Height
  - Weight
- Serious Infection (HIV, viral hepatitis, prion, etc)
  - *Use of new drugs* 
    - o Describe
  - Surgeries or other Procedures
    - Describe
- Diagnosis of any new condition
  - o Autoimmune (hypothyroid, ITP, RA, SLE, MS, celiac, Type I diabetes, Sjogrens)
  - o Asthma
  - Allergy/atopy
  - Metabolic disease
    - Diabetes II
    - Obesity
  - o Psychiatric disorder
  - Neurologic disease
    - Parkinson's disease
    - Amyotrophic lateral sclerosis (ALS)
    - Autism spectrum diagnosis
  - Cardiovascular disease
    - Myocardial infarction
    - Coronary artery revascularization
    - Cerebrovascular accident
    - Hypertension
  - o Colon cancer
  - Other malignancy
  - Inflammatory bowel disease
    - Crohn's
    - Ulcerative colitis
    - IBD-U
  - o IBS
- IBS-C
- IBS-D
- IBS-M
- o Other
- Hospitalization
  - o Reason for hospitalization
  - o FMT related (related, possibly related, unrelated)
- Life-threatening illness
  - o Describe/diagnosis
  - o FMT related (related, possibly related, unrelated)
- Death
  - Cause of death
  - o FMT related (related, possibly related, unrelated)

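### Section 8.3 compares registry outcomes with claims outcomes although the two sources ascertain events differently, and covariate adjustment does not remove a difference in capture

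*Protocol*

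**What the plan says.** Section 8.3 of the protocol adds a control group with recurrent CDI, "identified from insurance claims using Optum Insight Life Sciences, Inc data". The same source supplies the control outcomes: "Using these data, we can determine the incidence of relevant outcomes in a group of patients with recurrent CDI treated with antibiotics". The section then states: "The incidence of relevant outcomes in this group can be compared to the patients treated with FMT in the registry". The reason given is to strengthen the study of adverse events that were not anticipated. The worked example is survival: 4,313 controls with mean follow-up of 1.70 years, an equal FMT group with equal follow-up, and 90% power for a hazard ratio of 0.77.

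Registry outcomes are obtained in another way. Section 6.1 says: "Adverse event information will be provided by the FMT provider site at four time points post-FMT". These are months 1, 6, 12 and 24. Section 5.1 adds that "patients will then provide data annually up to 10 years". Supplement 6, which includes death, hospitalization and new diagnoses, is collected "up to 2 years by physician report and 10 years by patient report". Section 9.1 describes the late contact: "For follow-up beyond 2 years, the ePRO system allows the registry staff to automatically contact the patient".

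The protocol describes no linkage of registry patients to claims or death records. The regression and propensity methods in section 8.3 are introduced for comparisons between delivery methods.

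**The concern.** A comparison of incidences assumes that an event has about the same chance of being recorded in either group. Here the instruments differ. A hospital stay away from the FMT site enters the registry only if the site or the patient learns of it and reports it. An event in a control counts only if it leaves a usable record in the claims extract. If these chances differ, the ratio moves away from 1 with no effect of treatment. A larger sample does not help; it makes a false difference more likely to reach significance. Balancing age, comorbidity or indication does not help either, because the error lies in the outcome and not in the covariates.

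Death is the sharpest case because section 8.3 uses it as its example. After 2 years the only scheduled registry report comes from the patient, who cannot report his or her own death. On the control side, the mortality figures in section 8.3 come from life tables, so the text does not show that the claims source records deaths.

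Safety is the primary objective (section 2.1), and the claims cohort is the only group without FMT. A ratio that partly reflects capture could be read as a safety signal or as reassurance.

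**Working it through.** **Inputs from section 8.3:** 4,313 per group; 1.70 years; 90% power; hazard ratio 0.77; annual death probability 1.75%; expected survival 18.8 years. **Assumed:** two-sided alpha 0.05 (not stated for this calculation), exponential survival, 1:1 allocation.

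**Step 1. The plan's own figure.** Expected deaths per group are n × (1 − exp(−rate × 1.70)), and power is Φ(√(d/4) × |ln HR| − 1.96), with d the total deaths.

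- Rate 1/18.8 = 0.0532 per year: controls 4,313 × 0.0865 = 373; FMT group at 0.77 times the rate, 290; d = 663. Power = Φ(12.87 × 0.2614 − 1.96) = Φ(1.405) = 92%. The stated 90% is reproduced.
- Rate from the 1.75% annual probability, −ln(0.9825) = 0.0177: 127.5 + 98.5 = 226 deaths, power 50%.

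The two mortality inputs in the same sentence therefore do not agree. That is a separate matter. Here it means that the effect of unequal capture has to be shown at both rates.

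**Step 2. Effect of capture on the ratio.** Let the true ratio be 1, case mix similar, the event uncommon, and neither source record false events. Then

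observed ratio ≈ registry capture / claims capture.

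The documents give no capture figures, so the following pairs are assumptions. Each gives about 0.77: registry 73% with claims 95% (0.77 × 0.95 = 0.73); 69% with 90% (0.77 × 0.90 = 0.69); 62% with 80% (0.77 × 0.80 = 0.62). The reverse is equally possible: complete capture in the registry with 90% or 80% in claims gives 1/0.90 = 1.11 or 1/0.80 = 1.25.

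**Step 3. Chance of a false significant difference in deaths.** Take claims capture as complete and registry capture as c. Then d = n × p × (1 + c), where p is the control death risk over 1.70 years, and the chance is Φ(z − 1.96) + Φ(−z − 1.96) with z = √(d/4) × |ln c|. Example at 1/18.8 per year with c = 0.90: d = 373 × 1.90 ≈ 708, z = 13.30 × 0.1054 = 1.40, chance 29%.

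| Relative capture c (assumed) | Apparent HR | Chance at 1/18.8 per year | Chance at 1.75% per year |
|---|---|---|---|
| 0.95 | 0.95 | 11% | 7% |
| 0.90 | 0.90 | 29% | 13% |
| 0.85 | 0.85 | 57% | 24% |
| 0.80 | 0.80 | 82% | 39% |
| 0.77 | 0.77 | 92% | 50% |

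The nominal figure is 5%. If claims under-capture by the same share, the chances are the same and the apparent ratio is 1/c.

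In counts, c = 0.77 means 0.23 × 373 = 86 missed deaths at the higher rate, or 0.23 × 127.5 = 29 at the lower.

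**The case against.** Four objections carry weight.

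- Outcome lists, definitions and sensitivity analyses often sit in an analysis plan, which is not shown. Section 8.3 says only that incidences can be compared, and it fixes no test. This stands as a limit on the point. It does not remove it, because the two data sources are set in the protocol and the comparison is presented as feasible, with a power statement and no caveat.
- Registry capture is better than four forms suggest. Death and hospitalization are predefined fields in Supplements 5 and 6, sections 3.1 and 6.1 provide direct patient contact at least annually, and section 6.4 records spontaneous reports. The controls' mean follow-up of 1.70 years lies inside the period of provider forms, although its spread is not given. This stands: the early gap may be small.
- A negative-control admission ratio does not isolate capture. It also reflects remaining differences in age or frailty. This stands, so it serves as a check and not as a correction.
- Confining the comparison mainly to inpatient stays and barring tests on everything else would work against the aim of finding unanticipated events. This stands, and no such ban is proposed.

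A reader might also infer that 0.77 is the effect the plan sets out to detect. It is introduced as an example of what the sample could detect. Nor do the documents support the inference that symptoms or weight change will be compared with claims: these are registry fields, but section 8.3 never assigns them to this comparison.

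**Conclusion.** The point holds. The protocol fixes two different outcome instruments and sets their incidences side by side, and the adjustment methods it names cannot correct unequal capture. A false difference can therefore arise from following the text as written.

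Its size is unknown, because the documents give no capture rates for either source. On the assumed values above, relative capture of 0.90 raises the chance of a false significant survival difference from 5% to between 13% and 29%, depending on which of the protocol's mortality inputs is used. Relative capture of 0.80 raises it to between 39% and 82%. These figures assume no true effect, similar case mix and no false events.

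The direction is also unknown. A reader might conclude that FMT will look safer than it is. The documents do not show which source captures more, so that conclusion is not supported. Within 2 years the problem is limited by the provider forms; for death it grows after that. The text should be changed before the comparison is made, but the control cohort need not be dropped.

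**What to change.** Amend section 8.3 as follows.

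1. Make the primary FMT-versus-claims comparison on outcomes that both sources can record as the same event, under one common definition. Examples are hospital admissions and coded new diagnoses such as myocardial infarction, malignancy or diabetes. Limit it to the first 2 years, when provider forms are scheduled.
2. Include death only after confirming that the claims source records deaths.
3. Beside these results, report a negative-control ratio for admissions unrelated to the gut or to FMT, trauma for instance. The registry already has the field "Reason for hospitalization". Present the ratio as a check on unequal capture and residual case-mix difference, and do not use it to correct the other results.
4. Label comparisons of other outcomes as exploratory, and state differential ascertainment as a limitation.

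The cost is new wording in section 8.3, one additional analysis, and a check of what the claims source records about deaths. The registry's reason for hospitalization is listed without a coding scheme, so it would have to be mapped to claims codes. The primary comparison will cover fewer outcomes; the exploratory label keeps the others available for signal detection.

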## **PROTOCOL SUMMARY**

This document complies with requirements of the Declaration of Helsinki, International Harmonized Standards: EN ISO 14155-1 and ISO 14155-2:2003(E) and with 21 CFR Parts 50, 54, 56, and 812.

Title: Fecal Microbiota Transplantation National Registry

**Précis:** A national data registry of patients receiving fecal microbiota

transplantation (FMT) or other gut-related-microbiota products designed to prospectively assess short and long-term safety and

effectiveness

**Mission:** To expand knowledge and optimize practice in the

transplantation of fecal microbiota or other gut-related-

microbiota products.

**Goals:** To assess short-term and long-term safety

To assess effectiveness

To gather information on practice in North America.

To promote scientific investigation

To aid practitioners and sponsors in satisfying regulatory

requirements

10 years

**Population:** All patients receiving FMT or other gut-related-microbiota

products and the donors providing specimens for the enrolled patients' FMT. Patients will be enrolled regardless of race,

gender, ethnicity, or age.

**Number of Sites:** 75

**Number of Patients** 4,000

Subject

Participation
Duration:

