## 3 STUDY DESIGN

## 3.1 Overview Study Design Summery

This registry will prospectively enroll 4,000 patients who undergo FMT at 75 sites throughout North America. Information on FMT methodology employed (e.g., screening of donor and recipient, preparation, FMT delivery) will be collected from each site. The indication for FMT as well as baseline information on recipient will also be collected. Following FMT, patients will be followed at regular intervals up to 10 years post FMT. This will include follow-up information from the patient's healthcare provider at 1 month, 6 months, 1 year, and 2 years after FMT as well as direct communication with patients at least annually up to 10 years after FMT. Follow-up information collected will be designed to assess potential short-term and long-term safety and effectiveness.

Anticipating changes in therapy from current FMT to use of other gut-related microbiota products in coming years, the Registry will be constructed with the flexibility to collect methodological and follow-up clinical information for all forms of gut-related-microbiota products and for a variety of indications besides CDI and IBD.

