## 4 STUDY ENROLLMENT

## 4.1 Subject Inclusion Criteria

Participants will be eligible for participation regardless of age, race, ethnicity, or gender. Pediatric patients may participate if consent is given by a guardian.

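### Section 8.3 does not limit the FMT side of the claims comparison to recurrent CDI and ties its adjustment text to delivery-method comparisons, so case mix could bias the result in either direction

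*Protocol*

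**What the plan says.** Protocol section 8.3 adds "a retrospective control group of patients with recurrent CDI identified from insurance claims", to help study unanticipated adverse events. The control definition is tight: a physician diagnosis of CDI and three antibiotic courses at least 10 days apart, at least one of them vancomycin or fidaxomicin, with the third started within 90 days of the diagnosis. The size is given as: "We identified 4,313 patients meeting this definition with mean follow-up of 1.70 years". The median control age is 68.

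The FMT side is described in one sentence: "The incidence of relevant outcomes in this group can be compared to the patients treated with FMT in the registry". No indication, age or severity limit is attached to it.

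The registry itself is broad:
- The Protocol Summary defines the population as "All patients receiving FMT or other gut-related-microbiota" products.
- Section 4.1 states: "Participants will be eligible for participation regardless of age, race, ethnicity, or gender". Children may join with a guardian's consent.
- Section 3.1 builds in flexibility "for a variety of indications besides CDI and IBD".
- Supplement 3 lists IBD, IBS, constipation, obesity, diabetes, metabolic syndrome, fatty liver disease and neurologic disorders as well as CDI. Within CDI it separates refractory, recurrent and severe disease.

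The example power statement claims 90% power for a survival hazard ratio of 0.77, assuming equal numbers and equal follow-up in the two groups. The next paragraph of 8.3 turns to delivery-method studies. It is there that the protocol says "Comparative effectiveness studies rely on the ability to adequately account for differences between the treatment groups" and names logistic and Cox regression, propensity scores and risk scores, resting on covariates collected in the registry.

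**The concern.** Every control has recurrent CDI. As written, the FMT group may include patients with other diseases, other forms of CDI and very different ages. A difference in death or new diagnoses between such groups mixes any effect of FMT with the effect of who was treated.

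Modelling alone cannot repair this. No control lacks recurrent CDI, so there is no overlap on indication from which to estimate an adjustment for it. The restriction has to come from how the comparison population is defined.

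The protocol recognises the general principle but states it for comparisons between delivery methods. It does not state it for the comparison in which disease mix, treatment and data source can all differ. The claims cohort is also the only group not treated with FMT that the protocol describes. Bias here could produce an apparent benefit, or hide a harm, in a registry whose primary objective is safety.

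**Working it through.** **1. The plan's own figure.** The inputs from 8.3 are 4,313 controls, an equal number of FMT patients, mean follow-up of 1.70 years, expected survival of 18.8 years and a hazard ratio of 0.77. Alpha is not stated for this calculation; I assume 0.05 two-sided. With exponential survival and h = 1/18.8 = 0.0532 per year:
- Control deaths: 4,313 × (1 − exp(−0.0532 × 1.70)) = 4,313 × 0.0865 ≈ 373.
- FMT deaths: 4,313 × (1 − exp(−0.77 × 0.0532 × 1.70)) = 4,313 × 0.0673 ≈ 290.
- Total: about 663 events. Schoenfeld power is 92.0%, and about 616 events are needed for 90%.

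So 0.77 at 90% power is reproduced with this hazard. It is not reproduced with the 1.75% annual mortality quoted in the same sentence, which gives about 226 events and about 50% power. That is a separate matter, but it affects any restated figure (step 5).

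**2. The count.** Equal numbers means 4,313 FMT patients. The whole registry is 4,000, which is 313 fewer. The shortfall itself costs little, since power with 4,000 FMT patients is 91.1%. Its relevance is that a number above the full registry leaves no room for a recurrent-CDI subset.

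**3. Case mix with no FMT effect.** Let f be the share of FMT patients without recurrent CDI and r their death rate relative to controls. The protocol gives neither, so both are assumptions. Then crude HR ≈ 1 − f(1 − r), and reaching 0.77 requires f = 0.23/(1 − r).

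| r | f needed for 0.77 | crude HR at f = 0.10 | crude HR at f = 0.25 |
|---|---|---|---|
| 0.05 | 24% | 0.905 | 0.762 |
| 0.10 | 26% | 0.910 | 0.775 |
| 0.25 | 31% | 0.925 | 0.812 |
| 0.50 | 46% | 0.950 | 0.875 |

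If r is above 1, the same formula gives a crude hazard ratio above 1, so the sign of the bias is not fixed.

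**4. Masked harm.** Suppose the true hazard ratio in recurrent CDI is 1.25 and f = 0.25. Crude HR ≈ 0.75 × 1.25 + 0.25r. With r = 0.10 this is 0.9375 + 0.025 = 0.96. With r = 0.25 it is 0.9375 + 0.0625 = 1.00.

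**5. Price of restriction.** Keep 4,313 controls and 1.70 years, and let 90%, 75% or 50% of 4,000 FMT patients qualify. The shares are assumed.

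| FMT patients | power at HR 0.77, h = 1/18.8 | HR detectable at 90% power, h = 1/18.8 | same, 1.75% per year |
|---|---|---|---|
| 3,600 | 90% | 0.77 | 0.63 |
| 3,000 | 87% | 0.76 | 0.61 |
| 2,000 | 78% | 0.73 | 0.58 |

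These figures allow for no further loss from weighting or matching.

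**The case against.** The protocol never calls this comparison crude, and it does not use the word all for the FMT side. The sentence follows a description of recurrent CDI treated with antibiotics instead of FMT, which suggests two treatments for one disease. The adjustment model for an external control is commonly set in the SAP, which is not shown. The inference that the comparison will be unadjusted, or will use every registry patient, is therefore not supported: the text is silent on the first and merely unrestricted on the second.

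The illustration also depends on f and r. Section 1.2 says use outside unresponsive CDI needs an IND, and it treats CDI as the paradigm. Both point to a registry made up mostly of CDI patients, and at a 10% share the crude hazard ratio stays well away from 0.77. Nor is it documented that the FMT group would be younger or die less often. Patients treated for refractory or severe CDI could die more often than the controls.

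Finally, the main safety analysis in 8.3 is descriptive incidence with 95% confidence intervals. The claims cohort supplements it, and the 0.77 is offered as an example.

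All of this stands, and it limits the point. It does not remove it. The controls are restricted by disease and the FMT side is not, the power count admits no subset, and the adjustment text is attached to a different comparison. A model in the SAP could handle age and comorbidity. It could not adjust for an indication that no control has.

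**Conclusion.** The point holds as a mismatch of populations in 8.3, with adjustment left unstated for the comparison that needs it. The possible bias is material but unknown in sign and size. Under assumed inputs, a share of about 24% to 46% without recurrent CDI, dying at 5% to 50% of the control rate, would yield the plan's 0.77 with no FMT effect. A 10% share would yield only 0.91 to 0.95. A true hazard ratio of 1.25 could be hidden at a 25% share.

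A reader might infer that case mix will create a false benefit, or that the primary safety results are compromised. The documents support neither: they give no indication mix or registry mortality, and the descriptive incidence estimates do not use the claims cohort. This is a change the protocol should make. It does not undermine the registry as a whole.

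**What to change.** In section 8.3:
- Restrict the FMT side of the claims comparison to recipients treated for recurrent CDI who meet the control definition as nearly as registry data allow. Supplement 3 already records the indication, number of CDI episodes and prior treatment courses. It lists no course dates, so the 10-day and 90-day rules may be only approximated.
- State that propensity-score or regression adjustment applies to this comparison, for age, sex, comorbidity and prior courses so far as both sources hold them.
- Restate the detectable hazard ratio for the restricted FMT number, and say which mortality figure it uses.

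The change needs protocol wording and some analysis work, and no new data collection. The downside is a smaller FMT group and a slightly less favourable detectable hazard ratio: about 0.77, 0.76 or 0.73 at 90% power if 90%, 75% or 50% of 4,000 qualify, on the 1/18.8 per year hazard that reproduces the plan's figure.

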## 8 Statistical Plan

## 8.1 Sample Size Determination and Power

As noted in the AHRQ's Registry User's Guide, registries are used to provide precise estimates of outcomes in real-world practice and document that potential adverse events occur at less than a pre-specified incidence with a predefined level of confidence. Plans for the FMT registry include a sample size of approximately 4,000 patients, which will provide precise estimates of incidence rates for common and rare events. For example, if the incidence of an outcome after FMT in the Registry population is 5.0%, the 95% CI will be 4.4% to 5.7%, indicating a precise estimate of treatment effect. The planned sample size will also provide high confidence in ruling out rare adverse events. If an adverse event does not occur in the planned population of 4000 patients, we will have 95% confidence that the adverse event occurs at a rate of less than one in a thousand patients undergoing FMT.

The FMT registry also will support comparative effectiveness studies focusing on different methods of delivery of FMT (e.g., colonoscopy, enema, upper GI endoscopy, nasogastric or nasointestinal tube). Statistical power for comparative effectiveness studies will depend upon the incidence of the outcome and the distribution of use of the different methods of delivering FMT. For example, assuming an outcome that occurs in one out of 1,000 FMT procedures using one delivery method, there would be 90% power to detect a difference between an incidence of 0.001 and 0.008 assuming that 2,000 patients were exposed to each of the two delivery methods. For more common outcomes, the statistical power for specific relative risk estimate is greater. For example, with 2,000 patients in each group there would be 90% power to detect a difference between two approaches for which the incidence rates of events were 3% and 5% (i.e., RR=1.67).

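### The 90% power claimed for a mortality hazard ratio of 0.77 does not follow from the 1.75% one-year death risk quoted with it; at that risk power is about 50%

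*Protocol*

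**What the plan says.** Section 8.3 adds a retrospective control group with recurrent CDI treated with antibiotics, drawn from insurance claims: "We identified 4,313 patients meeting this definition with mean follow-up of 1.70 years". It then asserts: "The sample size should be sufficient to address questions on relatively rare outcomes". One worked example supports this. For a patient of the cohort's median age, 68, it gives two life-table figures: "the probability of death in the next 12 months is 1.75% and the expected survival is 18.8 years (CDC lifetables"). It continues, "assuming equal number of subjects undergoing FMT and equal follow-up time", that "we would have 90% power to detect a hazard ratio of 0.77 for a difference in survival rates between FMT and antibiotic treated patients".

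The section gives no alpha, sidedness, reference group for the hazard ratio, expected number of deaths or formula. It does not say which of the two life-table figures drives the power.

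**The concern.** Power in a survival comparison is governed by the number of deaths. With a yearly risk of 1.75% and follow-up of 1.70 years, roughly 3% of each group dies. A hazard ratio as close to 1 as 0.77 needs several hundred deaths, and 8,626 patients at that risk do not supply them.

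The example is the only number behind the statement that the claims comparison is large enough for relatively rare outcomes. If it is too favourable, a null mortality result could be read as stronger reassurance than the data can give, in a registry whose primary objective is safety. The stakes go no further: no sample size, analysis or stopping rule uses the figure.

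**Working it through.** **Inputs (section 8.3).** 4,313 per group; t = 1.70 years in both groups; 12-month death risk 1.75%; expected survival 18.8 years; HR 0.77; stated power 90%.

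**Assumption.** Two-sided alpha 0.05. This convention fits the two 90% power examples in section 8.1 (2,000 per group, pooled two-proportion test) better than one-sided 0.05:

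| Section 8.1 example | Two-sided | One-sided |
|---|---|---|
| 3% vs 5% | 89.8% | 94.3% |
| 0.001 vs 0.008 | 91.1% | 95.2% |

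**Formulas.** Deaths D = 4313·[1 − exp(−h·t)] + 4313·[1 − exp(−h·HR·t)]. Schoenfeld power = Φ(√(D/4)·|ln HR| − z), with |ln 0.77| = 0.2614 and z = 1.960 (two-sided).

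**1. Where the 90% can be found.** It appears when 18.8 years is converted to a constant hazard.
- As a mean: h = 1/18.8 = 0.0532 per year. D = 663 and power = Φ(√(663/4)·0.2614 − 1.960) = 92.0%. With 4,000 per group, D = 615 and power is 90.0%.
- As a median: h = ln 2/18.8 = 0.0369 per year. D = 465 and power is 80.5% (88.0% one-sided). With the hazard ratio inverted, D = 599 and power is 89.2% (94.0% one-sided).

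That this is how the figure arose is an inference; the protocol does not say. These hazards imply yearly death risks of 1 − exp(−0.0532) = 5.2% and 1 − exp(−0.0369) = 3.6%, against the 1.75% printed beside them for the same age. Life expectancy at 68 averages in the much higher death rates of later decades, so it cannot serve as the rate over the next 1.70 years.

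**2. Power at the printed 12-month risk.**
- h = −ln(1 − 0.0175) = 0.01765.
- Antibiotic group: 4313·[1 − exp(−0.01765·1.7)] = 127.5 deaths.
- FMT group: 4313·[1 − exp(−0.01765·0.77·1.7)] = 98.5 deaths.
- D = 226.
- Needed for 90%: 4·(1.960 + 1.2816)²/0.2614² = 615 (501 one-sided).
- Power = Φ(√(226/4)·0.2614 − 1.960) = 50.2%.

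The Freedman and two-proportion approximations both give 49.8%, and a simulation with 20,000 replicates gives 49.2%. With 4,000 FMT patients against 4,313 controls, D = 219 and power is 48.9%.

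**3. Other conventions at 1.75%.**

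| Where the 1.75% applies | Deaths | Two-sided | One-sided | Yearly risk needed for 90% (two-sided / one-sided) |
|---|---|---|---|---|
| Higher-risk group | 226 | 50% | 63% | 4.8% / 3.9% |
| Lower-risk group (other hazard = h/0.77) | 292 | 61% | 72% | 3.7% / 3.0% |

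The required risk is 1.7 to 2.7 times the printed one.

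**4. What is detectable.** At 1.75%, two-sided, 90% power is reached at HR 0.64, or 1.44 for an excess (0.67 and 1.40 one-sided). Holding HR 0.77, assumed yearly risks of 2.5%, 3.5% and 4.8% give 322, 450 and 615 deaths, and power of 65%, 79% and 90%.

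**5. Rising hazard and age spread.** A Gompertz curve passing through both printed figures has a slope of 0.0747 per year of age. If everyone is 68 it gives 232 deaths and 51% power. With ages normal around 68 (the SD is assumed, as the protocol gives none), HR 0.77, two-sided:

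| SD (years) | Deaths | Power | With ages stopped at 100 |
|---|---|---|---|
| 10 | 301 | 62% | 62% |
| 15 | 407 | 75% | 361 deaths, 70% |
| 18 | 500 | 83% | 381 deaths, 72% |

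**The case against.** The strongest reply is that the protocol prints two mortality figures and does not say it used the 1.75%. From 18.8 years as a constant hazard the 90% is nearly recovered, so this may be a poor exponential assumption and not a slip in arithmetic. That is probably right about the origin, but it does not rescue the figure: the rate it needs contradicts the 12-month risk in the same sentence, and over 1.70 years the 12-month risk is the relevant one.

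Second, the risk at the median age is not the cohort's average risk. Hazard rises steeply with age, so the average exceeds the value at 68, and patients with recurrent CDI may die at more than life-table rates. This stands: the true power is unknown and probably above 50%. The age-spread results stay below 90% for HR 0.77 two-sided, but that depends on the convention. In the same Gompertz model with the hazard ratio inverted and no upper age limit, SD 15 one-sided gives 91%, and SD 18 gives 90.5% two-sided and 95% one-sided. These are favourable corners; stopping ages at 100 brings the highest of them to 89%.

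Third, the sentence is offered as an example, and nothing in the design hangs on it. The 4,000 target in section 8.1 rests on precision and on ruling out rare events. That limits the consequence but does not make the figure correct.

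**Conclusion.** The point holds. At the 12-month death risk the protocol cites, power for HR 0.77 is about 50%, not 90% (226 deaths against 615 needed). It does not exceed 72% under any sidedness at alpha 0.05 or any direction of the hazard ratio. The 50% assumes two-sided alpha 0.05, equal groups of 4,313, exactly 1.70 years each, and a cohort dying at the life-table rate for age 68. It measures the gap between the stated power and the stated risk and does not estimate the cohort's real power, for which the protocol gives no death rate. The sentence should be corrected, but the effect is confined to what the FMT-versus-antibiotics mortality comparison can be said to detect.

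**What to change.** Replace the power sentence in section 8.3 with one based on a short-term death rate. State that rate and its source, alpha, sidedness, the reference group for the hazard ratio, follow-up and expected deaths. The best source is the crude death rate in the 4,313-patient claims cohort, if deaths are available there. Do not use 18.8 years as a constant hazard.

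If only the life-table risk is available, wording such as this would do:

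> At the life-table risk for the median age (1.75% in 12 months), with 4,313 per group, 1.70 years of follow-up and two-sided alpha 0.05, about 226 deaths are expected if the hazard ratio for FMT versus antibiotics is 0.77. Power is then about 50%; it reaches 90% at a hazard ratio of about 0.64, or about 1.44 for an excess. These values apply at that risk and are not the cohort's power.

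The power at assumed risks of 2.5%, 3.5% and 4.8% (about 65%, 79% and 90%) can be added to show the dependence. The sentence on sufficiency for relatively rare outcomes should then be brought into line with the new figure.

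The cost is one rewritten sentence, a less favourable number and, at most, one count of deaths in the claims data. No change to enrolment, visits or data collection is needed.
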